3.2 Study Outcomes

PRIMARY

- Maternal mean arterial blood pressure, defined as the highest MAP within 24 hour period

SECONDARY-SAFETY AND TOLERABILITY

- Liver toxicity, defined as 3x ULN of ALT or AST within 24 hours of study drug
- Maternal report of side effects
- Clinical parameters of maternal and fetal well being
- Composite neonatal outcome

Maternal or Fetal Parameter	Safety Endpoint
History	Headache unrelieved by oral analgesics
Physical examination	Abdominal tenderness, (right upper quadrant or epigastric)
Vaginal bleeding	Fall in hematocrit of $\geq 3\%$
Urine output	Oliguria (< 500 cc/24 hr)
Serum LFTs	AST and/or ALT $\geq 3x$ ULN within 24 hours of study drug
Fetal NST (or BPP)	Category III (or < 6)

SECONDARY-PHARMACOKINETICS

- Nicotinamide and metabolite concentrations in plasma at baseline, 2, 8, and 24 hours
- Peak plasma drug and metabolite concentration and time to reach peak
- Nicotinamide and metabolite elimination half-life
- Nicotinamide and metabolite area under the curve (integral of the plasma concentration-time curve)
- Nicotinamide and metabolite concentrations in urine at baseline, 8 and 24 hours

4 Subject Selection and Withdrawal

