4.4 Early Withdrawal of Subjects

4.4.1 When and How to Withdraw Subjects

Subjects may withdraw at any time and for any reason. Subjects may be withdrawn if they no longer meet eligibility criteria; or if in the opinion of the investigator it is not in the subject's best interest to continue. A subject may also be withdrawn if she experiences an unmanageable or irreversible adverse Grade 3 or 4 adverse event using the CTCA v3.0 criteria as defined in section on safety monitoring. The date of withdrawal from study participation will be recorded in the CRF. Subjects who either complete or are removed from the treatment phase at any time will have complete data chart abstracted and recorded for study purposes.

Specific study stopping rules include:

- Any maternal or fetal death deemed to be related or possibly related to study participation
- More than expected prevalence of liver toxicity within 24 hours of study drug, thus > 20% of subjects experience liver toxicity (more than 1 subject for every 5 subjects enrolled)
- More than expected prevalence of fetal side effects (defined as BPP < 6 OR UA Dopplers show absence or reversal of diastolic blood flow), (more than 1 delivery for fetal reasons per every 5 subjects enrolled)

Specific rules to stop study intervention for individual subject

- Delivery, or two weeks of treatment (“on-treatment” defined as within 24 hours of study drug)
- Liver toxicity (LFTs \geq 3x ULN within 24 hours of study drug)
- Maternal side effects that cannot be managed with oral medication

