All subjects will be included in the analysis, regardless of whether they received investigational agent. Subject demographic and baseline characteristics will be summarized. Descriptive summaries will include the number of subjects, mean, standard deviation, median, minimum and maximum for continuous parameters, frequency and percentages for categorical parameters.

8 Safety and Adverse Events

The PI and/or study staff will conduct daily medical monitoring for unanticipated problems, AEs, and serious AEs and record and report them to the UNC or WakeMed (respectively-dependent on where they are cared for) IRB and FDA as outlined below (Sections 8.2, 8.3, 8.5). The FDA will be notified after 1 case of liver toxicity and after every 1 case of delivery within 48 hours of enrollment, and will conduct ad-hoc review as they deem appropriate.

Study stopping rules and subject withdrawal for safety reasons are described previously (Section 4.4) and below (Section 8.4).

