8.4 Stopping Rules

The study will be stopped under the following circumstances:

- Any maternal or fetal death deemed to be related or possibly related to study participation
- >20% subjects experience liver toxicity (defined as AST or ALT \geq 3x ULN within 24 hours of study drug)

Specific rules to stop study intervention for individual subject

- Delivery, or 34 weeks, which ever occurs first
- Liver toxicity (LFTs \geq 3x ULN within 24 hours of study drug)
- Maternal side effects that cannot be managed with oral medication

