8.6 Data Safety Monitoring Board

The NC TraCS Data and Safety Monitoring Board will serve as the DSMB of record for this single center clinical study. The master protocol has been reviewed and approved. The DSMB monitor safety using *a priori* defined study stopping rules and rules for withdrawal of subjects. The DSMB will review data after every 6 enrolled subjects; the PI will notify the DSMB after every 2 cases of liver toxicity and after every 2 cases of delivery within 48 hours of beginning nicotinamide. The NC TraCS DSMB Charter is available for review.

9 Data Handling and Record Keeping

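### The fetal study-stopping rule appears in 4.4.1 but not in 8.4, and it defines one event while its limit counts another, so the same data can give opposite decisions

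*Combined protocol and SAP*

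**What the plan says.** Section 4.4.1 gives three study-level stopping rules.

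- **Death:** any maternal or fetal death judged related or possibly related to participation.
- **Liver toxicity:** the limit is "thus > 20% of subjects experience liver toxicity (more than 1 subject for every 5 subjects enrolled".
- **Fetal effects:** the event is "More than expected prevalence of fetal side effects (defined as BPP < 6 OR UA Dopplers show absence or reversal of diastolic blood flow", and the limit that follows is "more than 1 delivery for fetal reasons per every 5 subjects enrolled".

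Section 8.4 opens with "The study will be stopped under the following circumstances" and has two study-level items: related death (maternal or fetal) and ">20% subjects experience liver toxicity (defined as AST or ALT" at or above 3x ULN. It has no item on fetal findings or on deliveries for fetal reasons.

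The opening of Section 8 links the two places: "Study stopping rules and subject withdrawal for safety reasons are described previously (Section 4.4) and below (Section 8.4". It does not say that they differ or which one governs. Section 8.6 has the DSMB monitor safety with a priori "defined study stopping rules and rules for withdrawal of subjects" and review data after every 6 enrolled subjects. Section 6.2 leaves the indication for delivery and its timing to the primary obstetrician.

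**The concern.** There are two separate faults.

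First, the two lists of reasons to stop the study do not match. Someone applying 4.4.1 has a fetal rule. Someone applying 8.4 as a complete list has none short of a related fetal death.

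Second, even if 4.4.1 governs, its fetal rule cannot be applied in only one way. The event it defines is a test result, and the event its limit counts is a delivery. A woman can have the finding and stay undelivered. She can also be delivered for a fetal reason that the definition does not name. The liver rule beside it has neither fault: it appears in both lists and counts the event it defines.

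This is the study's only fetal stopping rule short of death. The board is meant to apply rules fixed in advance. A rule with two possible counts leaves the choice to be made after the data are seen.

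**Working it through.** **Is there a figure to reproduce?** The liver rule checks: more than 1 in 5 is more than 1/5 = 20%. The fetal limit is also more than 1 in 5. The rule speaks of more than the expected prevalence, but the documents give no expected fetal rate, so there is nothing to derive the limit from.

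**The lists side by side**

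| Study-level rule | 4.4.1 | 8.4 |
|---|---|---|
| Related maternal or fetal death | yes | yes |
| Liver toxicity above 20% | yes | yes |
| Fetal effects | yes | no |

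**The two readings of the fetal rule on the same data.** The rule is crossed when (events ÷ enrolled) exceeds 0.20.

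- *Example A:* 5 enrolled, 2 with BPP < 6 or absent or reversed diastolic flow, 1 of the 2 delivered for fetal reasons. Findings: 2/5 = 40%, stop. Deliveries: 1/5 = 20%, do not stop.
- *Example B:* 12 enrolled, 3 with findings, 2 delivered for fetal reasons. Findings: 3/12 = 25%, stop. Deliveries: 2/12 = 16.7%, do not stop.
- *Example C:* 5 enrolled, 2 delivered for a fetal reason outside the definition, for instance a Category III NST, and none with a defined finding. Deliveries: 2/5 = 40%, stop. Findings: 0/5 = 0%, do not stop.

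Neither count is therefore always the stricter one. These examples need no assumed rates.

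**How far apart the readings could be (illustration).** Assumptions, none of which is in the documents:

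- The fetal limit is checked at the DSMB reviews at 6, 12, 18 and 24 enrolled. Section 8.6 gives the interval of 6; Sections 3.1 and 7.1 give 24 women with preeclampsia.
- Women are independent, each with finding probability *p*.
- A fraction *q* of findings leads to delivery for fetal reasons and no other fetal deliveries occur, so the delivery probability is *pq*.

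The smallest counts above 20% are 2 of 6, 3 of 12, 4 of 18 and 5 of 24. At the first look, P(cross) = 1 − (1−p)^6 − 6p(1−p)^5:

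- p = 0.20: 1 − 0.2621 − 0.3932 = 0.345 (rounded)
- p = 0.10: 1 − 0.5314 − 0.3543 = 0.114

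Carrying the paths that have not crossed through the later looks by exact binomial recursion gives totals of 0.669 and 0.206. The full set is:

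| Finding rate *p* | Counting findings | Counting deliveries, *q* = 75% | *q* = 50% | *q* = 25% |
|---|---|---|---|---|
| 10% | 0.21 | 0.11 | 0.05 | 0.01 |
| 20% | 0.67 | 0.44 | 0.21 | 0.05 |
| 30% | 0.93 | 0.76 | 0.44 | 0.11 |

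**Sensitivity to the schedule.** The rule is worded per 5 subjects enrolled and is not tied to DSMB reviews. With *p* = 20% and *q* = 50% (delivery rate 10%), cumulative checks at 5, 10, 15 and 20 give 0.52 counting findings and 0.14 counting deliveries. A check after every subject from 5 to 24 gives 0.73 and 0.28. The levels move with the schedule, but a wide gap remains.

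**The case against.** The strongest defence is that Section 8 names 4.4 and 8.4 together, which reads most naturally as cumulative. On that reading the fetal rule survives its omission from 8.4. This has force, and it is why the status of the rule is arguable and not settled. It does not remove the conflict, because 8.4 is worded as the set of circumstances for stopping. The individual stopping rules differ between the same two sections as well (two weeks of treatment in 4.4.1, 34 weeks in 8.4). That suggests the lists drifted apart, and those passages also need reconciling.

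The fetal bullet might be meant as deliveries prompted by the listed findings. That is possible, but it is not what is written. The DSMB charter might settle both matters. It is not among the documents, and the protocol would still disagree with itself.

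Fetal events would not go unseen. The DSMB reviews data every 6 subjects and hears of every 2 deliveries within 48 hours of starting nicotinamide. The FDA is told of each delivery within 48 hours of enrollment. These are real safeguards, but they are not stopping limits.

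A reader might infer three stronger points that the documents do not support.

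- *That 8.4 has no fetal protection.* It stops the study for a related fetal death.
- *That the chance of a fetal stop is zero under 8.4, against as much as 0.93 under 4.4.1.* This assumes that 8.4 displaces 4.4.1, which Section 8 does not say, and it rests on assumed rates.
- *That the 3.2 table, with "Category III (or < 6" and no Doppler item, is a third conflicting stopping definition.* It lists safety outcomes, not stopping triggers, and may properly be wider or narrower than a stopping rule.

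**Conclusion.** The concern holds on two counts. The study-level stopping lists in 4.4.1 and 8.4 differ, and the documents do not say which governs. The fetal rule in 4.4.1 defines a test finding but sets its limit on deliveries, so identical data can mean stop or continue. The second is the more serious, because it remains even if 4.4.1 is taken to be in force and nothing in the documents resolves it.

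The size is clearest in the small examples: 40% against 20%, or 0% against 40%, among 5 women. The probabilities of about 0.67 and 0.21 illustrate the gap and are not estimates. They rest on an assumed 20% finding rate, half of findings leading to delivery, and checks at 6, 12, 18 and 24. The inconsistency itself rests on none of these.

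**What to change.** The sponsor and the DSMB should reconcile 4.4.1 and 8.4 so that both carry one identical list of study-level stopping rules, and should decide whether the fetal rule stands. Which clinical rule is right is for them to decide.

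If it stands:

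- name one countable event, either the test finding or the delivery for fetal reasons, so that the definition and the limit refer to the same thing;
- state the expected rate that the rule's wording relies on, and when the limit is checked;
- tabulate the other event descriptively at each DSMB review.

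The 3.2 outcome table need not be changed to match.

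The cost is a protocol wording change and a check of the CRF. Sections 3.1 and 6.2 plan chart abstraction of delivery and neonatal data and liver tests. They do not list BPP results, Doppler results or the indication for delivery, so capture of these should be confirmed.

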--	---

	
• Placental abruption defined as unexplained vaginal bleeding• Preterm labor defined as regular contractions and cervical change• Any condition deemed by the investigator to be a risk to mother or fetus in completion of the study• Any condition deemed by the investigator to require delivery within 48 hours 
Inclusion Criteria for healthy, normotensive, pregnant women
 
• Maternal age 18-45 years• Singleton or twin pregnancy with no known fetal anomalies (24 weeks to 33 weeks 3 days)• No known medical complications 
Exclusion Criteria for healthy, normotensive, pregnant women
 
• Current cigarette smoker• Hypertension requiring medical treatment• Diabetes requiring medical treatment• Pre-existing renal disease (creatinine \geq 1.5 mg/dL)• Any pre-existing medical condition that would increase risk for liver toxicity (e.g. hepatitis B or C; HIV; INH use)• Currently taking medication for a chronic medical condition• Currently taking an oral or IV antibiotic or antifungal medication 
Diagnosis and Inclusion Criteria for healthy nonpregnant women
 
• Age 18-45 years• No known medical complications or disease (eg hypertension, diabetes, liver or kidney disease) 
Exclusion Criteria for healthy nonpregnant women
 
• Current cigarette smoker• Hypertension requiring medical treatment• Diabetes requiring medical treatment• Pre-existing renal disease (creatinine \geq 1.5 mg/dL)• Any pre-existing medical condition that would increase risk for liver toxicity (e.g. hepatitis B or C; HIV; INH use)• Currently taking medication for a chronic medical condition (excluding oral contraceptives)• Currently taking an oral or IV antibiotic or antifungal medication
--	---

Study Product, Dose, Route, Regimen
	
Vitamin B₃-amide; 2.5 mg daily, administered as 1000mg at 8AM and 12MN; 500mg at 4PM, provided by Major Pharmaceuticals
 
[name] Advisor, Contracts and Billing [name] [name] Office: [contact] [contact] Email: [contact]

Duration of administration
	
Until delivery or 34 weeks' gestation

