3.1 General Design

This is an open labeled phase II study of vitamin B₃-amide dietary supplementation in pregnant women with early-onset preeclampsia, per ACOG guidelines. We will enroll 24 pregnant women at 24-33 weeks 3 days with EOP and anticipated treatment by expectant observation. If the woman is anticipated to remain undelivered for 48 hours after diagnosis she will receive vitamin B₃-amide, 2.5 mg/day dosed in the following manner: administered as 1000mg at 8AM and 12MN; 500mg at 4PM, continuing until delivery or 34 weeks, whichever occurs first. Optional research blood samples will be collected at times of clinically indicated blood draws (baseline and 2-3 times per week) to measure nicotinamide and its metabolite 2-pyridone, sFlt-1 and PIGF. A sample of cord blood will be collected (6ml) following delivery.

All study subjects will receive standard surveillance and treatment for expectant management of EOP, which may include but is not limited to:

- Daily prenatal vitamin
- 24-hr urine collection for protein excretion at admission
- Blood sampling for hematologic, liver, and kidney function at time of diagnosis and every 2-3 days thereafter
- Magnesium sulfate for seizure prophylaxis
- Betamethasone to accelerate fetal lung maturity
- Antihypertensive agents
- Twice weekly fetal surveillance by NST (30 minutes of continuous fetal heart rate monitoring) or BPP (30 minutes of ultrasound to monitor for fetal breathing, movement, fluid)
- Weekly ultrasound to measure amniotic fluid and UA Dopplers

In addition to above standard care for EOP, subjects will receive surveillance and treatment solely for study purposes, including:

- Daily administration of vitamin B₃-amide, 2.5 Gm/day in 3 divided doses; "on treatment" is defined as within 24 hours of dose
- Daily (M-F) study staff visit to query side effects if in-patient; with each outpatient visit (typically twice a week) if discharged from the hospital
- Optional blood sampling to coincide with clinical blood draws to measure sFlt-1, nicotinamide and 2-pyridone levels; chart abstraction to review liver function testing results (done clinically)
- Chart abstraction for maternal and delivery data (up until maternal discharge) and neonatal data (until 30 days of age or until discharge, whichever occurs first). We will

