5.2 Treatment Regimen

Subjects will receive vitamin B₃-amide dietary supplementation, 2.5Gm/day daily until delivery or 34 weeks' gestation whichever occurs first. “On-treatment” is defined as 24 hours of study drug.

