- Blood sampling at baseline (pre-dose), 2 hours post dose, 8 hours post dose and 24 hours post dose.
- Urine sample at baseline (pre-dose), 8 hours post dose and 24 hours post dose.
- This will be done either in the clinic or the CTRC

6.3 **Laboratory specimen handling procedures**

Blood for research purposes will be collected at the time of clinically indicated blood draws. Specimens will be labeled with the subject's unique study ID and processed.

Specimens to be tested for circulating sFlt-1 and PlGF levels will be stored and shipped as a single batch on dry ice to the research laboratory at Harvard University. The interassay coefficient of variance for sFlt1 and PlGF immunoassays ranges from 2.6% to 3.0%.

Specimens collected for nicotinamide and 2-pyridone measurements will be sent to the UNC School of Pharmacy Lab ([name]). [name] developed a LC-MS/MS method using protein precipitation (acetonitrile) to measure nicotinamide and 2-pyridone during our previous phase I study.

7 **Statistical Plan**

7.1 **Statistical Methods**

Sample size: The study sample size was calculated to the primary outcome of MAP. We stipulated *a priori* that $\alpha = .05$ and $\beta = 0.2$. Using the highest BP measured within each 24-hr period and applying the following formula we will calculate daily MAP:

$$\text{mean arterial BP} = [2(\text{diastolic BP}) + \text{systolic BP}] \div 3$$

Assuming that the mean (\pm sd) MAP at enrollment of our subjects is 107 (\pm 10) mm Hg, to detect a difference from enrollment to 48 hours after treatment of 7 mm Hg in MAP requires that 20 subjects be enrolled. We will enroll 24 to allow for 20% attrition due to delivery prior to 48 hours of treatment.

- We will use a repeated measurement ANOVA to compare baseline MAP to MAP at 48 hours, 7 days and weekly thereafter until delivery or 34 weeks.
- Maternal liver toxicity: the proportion of women who develop elevated liver function tests (ALT and/or AST \geq 3x ULN within 24 hours of study drug) will be determined and compared to expected proportion of 20%.
- Descriptive report of proportion of women with
 - Side effects
 - Fetal effects

7.2 **Subject Population(s) for Analysis**

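### Section 4.4.1 stops a woman's study drug at two weeks, while the Study Summary and Sections 3.1, 5.2 and 8.4 run it to delivery or 34 weeks, and nothing reconciles them

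*Combined protocol and SAP*

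**What the plan says.** Five places in the protocol say when an individual's study drug ends.

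- Section 4.4.1, in the list of rules for stopping the intervention in one subject: "Delivery, or two weeks of treatment". The bracket that follows only defines being on treatment as within 24 hours of a dose.
- Study Summary, duration of administration: "Until delivery or 34 weeks" of gestation.
- Section 3.1: "continuing until delivery or 34 weeks, whichever occurs first".
- Section 5.2: "daily until delivery or 34 weeks" of gestation.
- Section 8.4, in a list with the same heading as the one in 4.4.1: "Delivery, or 34 weeks, which ever occurs first". The other two bullets in the two lists agree.

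Two further sections presuppose treatment beyond two weeks. Section 7.1 compares baseline MAP with MAP at 48 hours, "7 days and weekly thereafter until delivery or 34 weeks". Section 12.3 pays for weeks 3 to 10 on study medication. The introduction to Section 8 refers the reader to both 4.4 and 8.4 without giving either precedence.

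Liver toxicity is tied to dosing. The study-stopping rule in 4.4.1 concerns "More than expected prevalence of liver toxicity within 24 hours of study drug", and the endpoint in 7.1 uses the same 24-hour window against an expected 20%.

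**The concern.** This is a contradiction between instructions, not a criticism of either duration. Stopping at two weeks would breach neither stop list but would depart from the dosing instructions in the Study Summary, 3.1 and 5.2. Continuing past two weeks would depart from 4.4.1. Staff cannot follow every passage for a woman who starts before 32w0d and is undelivered and on drug at day 14.

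Three things depend on the choice:

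1. Whether maternal and fetal exposure to the investigational agent ends or continues.
2. Whether weekly MAP values after day 14, which enter the repeated-measures ANOVA, are on-drug or off-drug. If staff resolve the conflict differently from case to case, the later time points would mix the two.
3. How long a liver enzyme rise can register, since both the endpoint and the study-stopping rule count only rises within 24 hours of drug.

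Adverse-event follow-up is shifted rather than lost: Section 3.1 sets a call 30 days after the last dose and another 30 days after delivery.

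**Working it through.** **Inputs.** Entry window 24w0d to 33w3d (Study Summary, 3.1). Two-week limit (4.4.1). 34-week limit (Study Summary, 3.1, 5.2, 8.4). Weekly MAP from day 7 (7.1). Liver function tests every 2-3 days (3.1, 6.2) or every 2-7 days (5.5). Payments (12.3).

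**The plan's own duration-dependent figures.** The longest possible treatment under the 34-week rule is 34w0d − 24w0d = 70 days = 10 weeks, matching the 10 weeks in 12.3. Payment is 4 × $20 = $80 (baseline, day 3 trough, day 3 peak, day 7) plus 8 × $20 = $160 (weeks 3-10), total $240, matching the stated maximum. The payment schedule was therefore built on the 34-week rule. Under a two-week limit the $160 cannot be earned.

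**Where the rules differ.** In days of gestation, the entry window runs from 168 to 234, which is 67 entry days, and 34w0d is day 238. The two-week rule stops drug earlier whenever 238 − entry > 14, that is, entry on days 168 to 223 (before 32w0d): 56 of 67 entry days. From 32w0d the rules agree.

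**Exposure and MAP time points.** Maximum days = min(14, 238 − entry) under one rule and 238 − entry under the other. Weekly MAP points = (238 − entry)/7, rounded down. Those after day 14 are that number minus 2 (days 7 and 14).

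| Entry | Max days, two-week rule | Max days, 34-week rule | Weekly MAP points | After day 14 |
|---|---|---|---|---|
| 24w0d | 14 | 70 | 10 | 8 |
| 28w0d | 14 | 42 | 6 | 4 |
| 30w0d | 14 | 28 | 4 | 2 |
| 31w6d | 14 | 15 | 2 | 0 |
| 32w0d | 14 | 14 | 2 | 0 |

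The first affected MAP point is day 21. That needs at least 21 days to 34w0d, so entry by 31w0d: days 168 to 217, or 50 of 67 entry days.

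**Liver tests that could count.** Take entry as day 0 and the window as closing one day after the last dose: day 15 under the two-week rule; day 71 (entry 24w0d) or day 43 (entry 28w0d) under the 34-week rule. Post-enrollment draws = window ÷ interval, rounded down.

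| Interval | Two-week rule | 34-week rule, entry 24w0d | 34-week rule, entry 28w0d |
|---|---|---|---|
| 2 days | 7 | 35 | 21 |
| 3 days | 5 | 23 | 14 |
| 7 days | 2 | 10 | 6 |

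If dosing instead occupies days 0 to 13, the window closes before a day-15 draw and the 3-day count under the two-week rule is 4 rather than 5. No other entry changes. All counts assume the woman stays undelivered and is sampled on schedule.

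**What is not affected.** The 48-hour and 7-day MAP comparisons lie inside two weeks, so they and the sample size of 20 (24 enrolled) do not depend on the rule.

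**The case against.** The strongest reply is that one bullet is out of line with several consistent passages, so readers will take 34 weeks as intended and treat 4.4.1 as leftover text. Section 1.4 lends this some weight: the Phase I study treated for up to two weeks. But the documents do not say the text was carried over, the protocol has no order of precedence, and the bullet is an operative stop rule. It could equally be a deliberate cap. Only the sponsor can say.

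A second reply is that few women will meet the conflict, and that 70 days needs a woman entered at 24w0d to stay undelivered for ten weeks. That is fair as to scale. Section 1.1 reports delivery within two weeks for 85% of women with an sFlt-1/PlGF ratio above 0.85 and 15% of those below. If those rates carried over to 24 enrolled women, between 24 × 0.15 ≈ 4 (all high ratio) and 24 × 0.85 ≈ 20 (all low ratio) would be undelivered at two weeks. Entries from 32w0d would lower this. Selecting women expected to remain undelivered for 48 hours could raise it. Even 4 of 24 is not negligible here.

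Third, liver tests are taken as clinical care, and the endpoint is a proportion of women, so five times as many possible draws does not mean five times as many events. That stands: the draw counts describe opportunity to detect, not expected toxicity. It is also true that the primary comparisons are untouched.

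**Conclusion.** The concern holds. Section 4.4.1 and the dosing instructions in the Study Summary, 3.1 and 5.2 cannot both be followed for a woman who starts before 32w0d and is undelivered and on drug at day 14, and Section 8.4 gives a different limit from 4.4.1 under the same heading. At the extreme the rules differ fivefold in maximum exposure; at 28w0d, threefold; at 30w0d, twofold; from 32w0d, not at all. These are upper limits that assume no earlier delivery or withdrawal, and the entry-day counts do not estimate how many women are affected. The conflict governs exposure, the liver-toxicity observation window and the status of MAP after day 14, so it should be resolved even though the main MAP comparisons are safe. Nothing here favors one duration over the other.

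**What to change.** Reconcile Section 4.4.1 with the Study Summary and Sections 3.1, 5.2 and 8.4 so that one end-of-treatment rule, decided by the sponsor, appears in every place. Then align with it:

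- the weekly MAP analysis in 7.1, stating whether values after the last dose are analysed and how;
- the observation window for the liver-toxicity endpoint and the 20% study-stopping rule;
- the timing of the call 30 days after the last dose (3.1);
- the payment schedule in 12.3.

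The cost is a short protocol amendment, its submission to the IRB as Section 11 requires, and a notice to the DSMB. No additional participants or data are needed.
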